FIOC was designed specifically to aid development of positive coparenting alliances between at-risk (unmarried, uncoupled, low income) African American mothers and fathers having a first baby together. In the RCT, randomly-assigned control group families (referred by already-known referral agents and partners who worked closely with our team on the pilot projects) will receive Pinellas County services as-usual for pregnant parents and assistance of a Resource and Referral Navigator for referrals to desired community services ("Treatment as Usual", or TAU). The remaining (experimental group) families will receive the same services and aid, plus the 6-session FIOC prenatal intervention with a post-natal booster session. The first 150 families consented in will be assigned to groups via urn randomization. The remaining families recruited up to 170 will be assigned to the experimental (FIOC) group to achieve balance in the number of families contributing postnatal follow-up data longitudinally in the two groups to allow minimally sufficient statistical power for analyses. The FIOC intervention addresses the importance of safe, healthy families for early infant development, the impact a cooperative and sustained coparenting alliance can have in promoting positive infant development, challenges unmarried parents face cultivating a coparenting alliance together when their commitment to one another as romantic or married partners is in doubt, and ways to surmount these obstacles, maintain rapport, and sustain a strong alliance.

All 170 participating families, both at intake (prior to the intervention) and then again at 3 and 12 months post-partum, will report beliefs about fatherhood; extent of depressive symptomatology; and quality of the mother-father partnership. State-of-the-field coparenting observations will be conducted at each follow-up, along with measures of parental stress, intimate partner violence (IPV), perceived coparenting support, father engagement, and infant socioemotional adjustment. Analyses will examine impact of the intervention on promoting more supportive, coordinated post-partum coparenting alliances and more positive adult and infant outcomes. Exploratory analyses will examine links between father involvement and child adjustment and whether this coparenting intervention also stands to prevent IPV.

2. Background information

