Child Outcome Measures at Time 3: An adapted version of the Infant Toddler Social Emotional Assessment (ITSEA; Carter & Briggs-Gowan, 2006), comprised of the full Brief Infant Toddler Social Emotional Assessment (BITSEA) and select additional scale items from the longer ITSEA instrument, was developed in consultation with the scale’s author. The instrument measures both social-emotional/ behavioral problems and delays in competency for children ages 12-36 months. It is a 71-item parent-report index constituting of six sub-scales: Problem behavior, competence, compliance, negative emotionality, aggression, and sleep.

5. Sample size justification:

We employed a computer program provided by Murphy et al. (2009; the same information is available from the tables in Cohen, 1988) to compute the significance level required for a projected sample size, incorporating attrition estimates, of $N=120$ (60 each in the treatment and control groups, respectively). Assuming the null effect hypothesis and alpha set at .05 and power of .8, an $F(1, 117)$ of 7.74 with a $d = .514$ is required for significance. Keeping the null hypothesis test, alpha .05 and lowering power to .5, an $F(1, 117) = 4.03$ with a $d = .37$ is required for significance. Drawing on effect size estimates from the feasibility study, even with low power (.5) resulting in a $d=.37$ we would be positioned to establish the effect of the FIOC treatment for 10 of the 12 FIOC variables (10 of the 12 SCID-evaluated couple problem-solving and communication variables summarized earlier had a d greater than .33).

6. Sample type or inclusion and exclusion criteria for participating in the research:

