## **Cover Letter**

### **Statistical Analysis Plan**

**Document Date 1.31.2022**

**NCT03097991**

### **FIOC Statistical Analysis Plan**

- Initial descriptive summations and simple statistical tests will compare groups.

- Primary Aims 1-4: Effects of the intervention. To examine if coparenting and individual adjustment outcomes are superior for FIOC families than for control group families at 3- and 12-months post-partum two-sided independent sample t-test for equivalence will first be employed for single time point comparisons. We will test hypotheses further using linear or generalized linear models to control for potential confounding and account for imbalance between the two treatment conditions.
- For longitudinal outcomes that are continuous (measured at Baseline; 3; and 12 months post-partum) we will use repeated measures analysis of covariance (ANCOVA; Crowder & Hand, 1990) to detect if treatment and control groups perform differently at any time points. For longitudinal outcomes that are categorical, generalized linear model (GLM, McCullagh & Nelder, 1989) will be used for the same purpose. Repeated measures ANCOVA and GLM allow us to account for correlation between repeated measures and detect possible moderating/confounding between treatment effects and subject individual differences. Multiple comparison adjustment will be addressed in analyses. We will report significance under both regular (.05) and Bonferroni-adjusted alpha.
- Exploratory Aim 1: To examine whether extent of father engagement is associated with better infant socioemotional adjustment regression analyses will examine variance in infants' 12-month ITSEA Internalizing, Externalizing, Dysregulation and Competence scores explained by 3- and 12-month father engagement.
- Exploratory Aim 2: To examine whether FIOC prevents the emergence of IPV and help to prevent future IPV in couples where it was previously reported, we will first explore simple chi-square analysis to compare FIOC and TAU conditions on the binary variable of any instance of physical violence between partners reported on the CTS2 over the 12 months of follow-up. Next,

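### Section 5 claims 80% power for 60 v 60 without saying how many FIOC families are randomised; the stated power appears to lean on non-randomised top-up families

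*Protocol*

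**What the plan says.** Protocol Section 5 (Sample size justification) works from a "projected sample size, incorporating attrition estimates, of $N=120", split as "60 each in the treatment and control groups, respectively". No attrition rate is given, overall or by arm. Two cases follow:

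- "alpha set at .05 and power of .8, an $F(1, 117)$ of 7.74 with a $d = .514$ is required for significance"
- "alpha .05 and lowering power to .5, an $F(1, 117) = 4.03$ with a $d = .37$ is required for significance"

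Section 5 relies on the second case to argue that most of the observed couple-communication variables from the feasibility study (10 of 12) are within reach.

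Protocol Section 1 (General Information) describes allocation in two stages. First: "The first 150 families consented in will be assigned to groups via urn randomization". Then: "The remaining families recruited up to 170 will be assigned to the experimental (FIOC) group". The reason given is "to achieve balance in the number of families contributing postnatal follow-up data longitudinally in the two groups", together with reaching the minimum power needed for the analyses.

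Protocol Section 4 (Study design) still describes every eligible family as being randomised to one of the two groups. The SAP, under Primary Aims 1–4, specifies a "two-sided independent sample t-test for equivalence will first be employed for single time point comparisons", followed by models that adjust for confounding and imbalance. It does not say whether the directly assigned families enter those comparisons, and it plans no analysis restricted to randomised families.

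**The concern.** The causal claim in Aims 1–4 rests on random allocation. Up to 20 FIOC families do not have it, and Section 1 says they were added for balance and for power. On its natural reading, the randomised FIOC families alone were expected to supply too little follow-up data. Section 5 nevertheless presents one figure for 60 v 60 and does not say how many of the 60 FIOC families are randomised.

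A reader would therefore credit the randomised comparison with 80% power at d = .514, when some of that power may come from families outside the randomisation. If so, the randomised comparison can reliably detect only a larger effect than stated, and a null result would be read as more informative than it is.

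**Working it through.** **Inputs from the documents.** 60 v 60 with data, alpha .05, d = .514 and d = .37 (Protocol Section 5). Two-sided test (SAP, Primary Aims 1–4; a 1-df F test is also two-sided). 150 families randomised and up to 170 − 150 = 20 assigned directly to FIOC (Protocol Section 1).

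**Assumptions, because the documents are silent.** A 75:75 split of the 150 (urn randomisation does not guarantee it), retention in each arm, and the number of top-up families among the 60.

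**Formula.** For n1 and n2 families with data, λ = d² × n1 × n2 / (n1 + n2). Power is the probability that a noncentral F(1, n1 + n2 − 2, λ) exceeds the central 95% point. Using Section 5's 117 error degrees of freedom instead of 118 changes power by less than .001.

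**Step 1: reproduce the plan's figure.** λ = .514² × 60 × 60 / 120 = 7.93; critical F = 3.92; power = .797. The printed d values also follow from the printed F values: 2 × √(7.74/117) = .514 and 2 × √(4.03/117) = .371. At d = .37, power is .520 against the stated .5 (exact 50% power needs d = .361). Section 5 is correct for its own inputs.

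**Step 2: how many of 60 FIOC families might be top-ups.**

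- Equal retention across all 95 FIOC families (75 + 20): 60/95 = 63.2%, so 75 × .632 = 47 randomised and 13 top-up families.
- All 20 top-ups retained: 60 − 20 = 40 randomised.
- Only 5 or 10 top-ups among the 60: 55 or 50 randomised.

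**Step 3: power of the randomised comparison with 60 TAU families.**

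| Randomised FIOC v TAU | Top-ups in the 60 | λ at d = .514 | Power at d = .514 | d for 80% power |
|---|---|---|---|---|
| 60 v 60 | 0 | 7.93 | .797 | .516 |
| 55 v 60 | 5 | 7.58 | .779 | .528 |
| 50 v 60 | 10 | 7.20 | .758 | .541 |
| 47 v 60 | 13 | 6.96 | .744 | .551 |
| 40 v 60 | 20 | 6.34 | .703 | .578 |

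For Section 5's second case, power at d = .37 falls from .520 to .469 (47 v 60) or .434 (40 v 60). The d giving 50% power becomes .385 or .404.

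**Step 4: relax the 60 in TAU.**

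- TAU retains more than 60: 50 v 70 gives .786, 55 v 65 gives .795 and 55 v 68 gives .803.
- One retention rate for all 170 families, yielding 120 in total: 120/170 = 70.6%, so 75 × .706 = 53 per randomised arm, and 53 v 53 gives .746.
- 80% retention of the 150: 150 × .80 = 120, or 60 v 60 with no top-up, and power stays at .797.

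**The case against.** A reader might infer two stronger conclusions: that FIOC reaches 60 only by counting non-randomised families, and that the randomised comparison therefore has 70–74% power. The documents support neither as fact. Section 5 ties its 60 per arm to neither 150 nor 170, and 80% retention of 150 gives exactly 60 v 60. Balance alone could also prompt a top-up: if TAU kept 68 and randomised FIOC kept 60, families might still be added to even the arms, although the randomised comparison would have power of .82. The 70–74% needs TAU at 60 and 13 to 20 top-ups inside the FIOC 60; neither is documented. For the same reason, 40–47 v 60 should not be written into the protocol as though those were trial counts.

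Nor is there an arithmetic error in Section 5, which reproduces for the inputs it states. The larger problem may be that non-randomised families could enter the main comparison, which restating power does not cure. The loss is modest, and the protocol itself claims only minimum power.

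All of this limits the size and certainty of the point. It does not remove it. Balance is only half of the reason Section 1 gives; the other half is power, which implies that the randomised families alone were thought insufficient. The no-top-up scenario fits poorly with that. Section 5 still does not say which families its 60 contains.

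**Conclusion.** The point holds in conditional form. Section 5's 80% is right for 60 v 60, but it is not shown to describe the randomised comparison, and Section 1 suggests that it depends partly on directly assigned families.

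With TAU held at 60, the shortfall at d = .514 runs from about 2 points (5 top-ups among the 60) to about 9 points (20 top-ups: .797 − .703 = .094). If TAU retains more than 60, there may be almost none. The documents do not say which case applies, because they give no attrition by arm and no count of randomised FIOC families with data. This is an omission that affects how a null result is read; it does not invalidate the trial.

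**What to change.** 1. In Protocol Section 5, state how many of the 60 FIOC families are randomised, and give attrition by arm.
2. Restate power and detectable d for randomised families only, using the trial's own counts with follow-up data in each arm. If those are not available, give the conditional range above with its assumptions shown.
3. In the SAP, make the randomised-only comparison the basis of the causal claim for Aims 1–4. Present the 60 v 60 comparison that includes top-up families as supplementary and non-randomised.
4. Reconcile Protocol Section 4, where all eligible families are randomised, with Section 1, where up to 20 are not.

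The cost is redrafting plus one extra analysis set from data already collected; no further families are needed. The drawback is that the stated power becomes less favourable by up to about 10 points.

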6. Mother-Father Conflict and Collaboration during Coparenting Discussions. Evaluated using a paradigm validated in the PI's prior coparenting studies. Father and mother discuss areas of current child-related disagreement or uncertainty (e.g., overnights; paternal support; childcare; child temperament concerns; involvement of other kin caregivers; complications of children from prior unions). Raters observe and rate videotaped discussions using Lindahl and Malik's (2000) System for Coding Interactions in Dyads (SCID). In the feasibility study, statistically-significant improvements were seen in SCID ratings of (increased) problem-solving communication; (increased) mother-father cohesion; and (decreased) coerciveness

Outcome Variables: Family and Child Measures Taken at Times 2 and 3 Only

1. Parenting and Coparenting Adjustment. Two sets of coparenting indicators and one parenting measure not yet possible to evaluate at Time 1 will be obtained as Time 2 and 3 outcome measures:

a) Coparenting: Felt Coparenting Support: Reported by both mothers and fathers, and assessed using Abidin and Konold's (1999) 20-item Parenting Alliance Measure (PAM). The PAM is a five-point self-report scale (1 = strongly disagree; 5 = strongly agree), which evaluates how cooperative, communicative and mutually respectful parents are with regard to caring for the baby.

b) Coparenting: Observed Coparenting Behavior during Trilogue Interaction. All families are assessed at 3-months and at 12-months post-partum in Fivaz-Depeursinge and Corboz-Warnery's Lausanne Trilogue Play. The LTP has 4 parts: (a) first one parent plays with baby, other parent just present; (b) parents switch roles; (c) all 3 family members play together; (d) parents active and baby placed in the third party position. Coparenting during the LTP at 3 months postpartum is to be evaluated using the 3-month version of the Coparenting and Family Rating System (McHale & Coates, 2015). The standard CFRS is to be used to evaluate 12-month coparenting during the LTP.

c) Degree of Parenting Stress: Reported by both mothers and fathers, and assessed using a 36-item Parenting Stress Index-Short Form, validated in a low-income, African American population (Reitman et al. 2002). The PSI-SF has 36 items from the original 120-item PSI. Items are identical to those in the original version and yields scores on the following subscales: 1) Parental Distress, 2) Parent-Child Dysfunctional Interaction, and 3) Difficult Child

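### Section 5 presents the effects detectable at 80% and 50% power as significance thresholds, and its ten-of-twelve claim rests on 50% power and a .33 cut-off that does not match its own .37

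*Protocol*

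**What the plan says.** Protocol Section 5 (Sample size justification) projects N = 120 after attrition, 60 per arm. The first calculation begins "Assuming the null effect hypothesis and alpha set at .05 and power of .8" and arrives at F(1,117) = 7.74 and d = .514. The second begins "Keeping the null hypothesis test, alpha .05 and lowering power to .5" and arrives at F(1,117) = 4.03 and d = .37. Both pairs are described as the values needed for significance.

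From the second pair the protocol concludes that "we would be positioned to establish the effect of the FIOC treatment for 10 of the 12 FIOC variables". The support, in parentheses, is that ten of the twelve SCID problem-solving and "communication variables summarized earlier had a d greater than .33". Neither document lists the twelve values.

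Three other places bear on this:

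- Protocol Section 1 assigns the families beyond the first 150, up to 170, to FIOC to balance the numbers with follow-up data, "to allow minimally sufficient statistical power for analyses".
- The SAP, under Primary Aims 1-4, says that a "two-sided independent sample t-test for equivalence will first be employed for single time point comparisons", followed by adjusted models.
- The SAP bullet on longitudinal outcomes adds: "We will report significance under both regular (.05) and Bonferroni-adjusted alpha".

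**The concern.** At a fixed alpha and fixed degrees of freedom there is one critical F. Two different values at the same alpha and N cannot both be significance thresholds, so at least one label is wrong.

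The ten-of-twelve sentence then treats a roughly even chance per test as enough to establish ten effects. It also compares the pilot results with a lower cut-off (.33) than the one just derived (.37).

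This is the only power calculation in the two documents. Section 1 appeals to sufficient power when it assigns the last families without randomization, so a reader needs to know what power the plan regards as sufficient and for what effect. Someone taking .514 as a significance cut-off, or 50% power as adequate, could misread a null result.

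**Working it through.** **Inputs.** Protocol Section 5: 60 per arm, alpha .05, error df 117, the pairs 7.74/.514 and 4.03/.37, and the .33 cut-off. Tests are two-sided: an F test with one numerator df is two-sided, and the SAP names a two-sided t-test. The baseline-outcome correlation r and the number of tests m are not given, so they are assumed over a range.

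**1. Reproducing the plan's conversions.** d = 2·√(F/117).

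- F = 7.74: 2·√(7.74/117) = .514
- F = 4.03: 2·√(4.03/117) = .371

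Both match the protocol.

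**2. What significance requires.** The 95th percentile of central F(1,117) is 3.92. This corresponds to an observed d of 2·√(3.922/117) = .366, or √(3.922/30) = .362 by the two-sample formula, so about .36 to .37. An observed F of 7.74 has p = .0063, and an observed F of 4.03 has p = .047. The first is about twice the threshold (7.74/3.92 ≈ 2.0); the second is close to it.

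**3. What .514 and .37 are.** Power comes from the noncentral t with 117 df and noncentrality d·√30/√(1 − r²). At r = 0 the noncentrality is .514 × 5.477 = 2.82, giving power .797, and .37 × 5.477 = 2.03, giving power .520. They are therefore the effects detectable with about 80% and 50% power. The 50% figure lies near the significance threshold because an effect equal to the threshold is exceeded about half the time.

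**4. Power at the values in the ten-of-twelve claim.**

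| Assumed r | Power at d = .33 | at .37 | at .514 | d for 80% power |
|---|---|---|---|---|
| 0 | .434 | .520 | .797 | .516 |
| .5 | .544 | .641 | .897 | .447 |
| .7 | .709 | .804 | .974 | .368 |

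The expected number of significant results among ten tests is 10 × power, which does not require independence. At r = 0 it is 4.3, 5.2 and 8.0 if all ten true effects equal .33, .37 or .514. These illustrate the cut-offs; they do not forecast this trial. At r = 0, 80% power needs about 116 per arm for d = .37 and 146 per arm for d = .33.

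**5. Bonferroni alpha, .05/m.** The d needed for 80% power is:

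| Assumed r | m = 2 | m = 12 | m = 24 |
|---|---|---|---|
| 0 | .569 | .689 | .730 |
| .5 | .493 | .597 | .633 |
| .7 | .406 | .492 | .522 |

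**6. What the pilot d values measure.** Section 5 does not say. Section 4, on the coparenting discussions, reports that "In the feasibility study, statistically-significant improvements were seen in SCID ratings", and Section 2 lists random selection among the main differences from the earlier studies. That suggests pre-post changes, which need not equal between-arm effects. This is an inference, because the pilot design is not stated.

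**The case against.** The best defence has four parts.

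- **The arithmetic is right and the low power is disclosed.** The conversions reproduce, the 80% value is printed first, and the sentence with the claim itself calls the power low. This stands as far as it goes: the label is materially wrong only for 7.74/.514. Disclosure does not make about 50% power per test enough to establish ten effects.
- **Baseline adjustment may rescue the claim.** The twelve variables are SCID ratings, taken at baseline, 3 and 12 months, and for continuous outcomes on that schedule the SAP specifies repeated measures ANCOVA. Error df of 117 rather than 118 also fits one covariate. At r = .7, d = .37 does have 80% power. This is a real possibility, but no correlation is stated. The SAP's first-listed comparison is an unadjusted t-test, and several coparenting and parenting outcomes cannot be measured at baseline.
- **The pilot effects may be well above .33.** The text gives only a lower bound, and at r = 0 a true d of .6 would have power .90. This stands, and it is why the shortfall cannot be sized from the documents.
- **No test or sample size would change, and Section 1 does not cite Section 5 or a power level.** Both are true. The link to Section 1 is that it invokes sufficient power when the documents define power nowhere else. The requests about Bonferroni and the type of d concern missing detail and are secondary.

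**Conclusion.** The concern holds. Section 5 mislabels detectable effects as significance thresholds. The error is material for 7.74/.514, against a true critical F of 3.92, and numerically slight for 4.03/.37.

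The ten-of-twelve claim rests on about 50% power and on a cut-off that does not match the value derived for it. It is unsupported rather than shown to be false, since all ten pilot values could exceed .37.

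At the planned 60 per arm and alpha .05, 80% power needs a true d of about .52 with no baseline gain, about .45 if r = .5 and about .37 if r = .7. The correlations are assumptions. The .33/.37 mismatch and the mislabelling do not depend on them.

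**What to change.** In Protocol Section 5:

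1. Relabel 7.74/.514 and 4.03/.37 as effects detectable with about 80% and 50% power, and state the significance threshold once (F = 3.92).
2. State that 80% power at .05 needs a true d of about .52 without baseline adjustment. Give any smaller value only with the baseline correlation it assumes.
3. Reconcile .33 with .37.
4. Delete the ten-of-twelve claim, or restate it at 80% power with the twelve pilot values listed.
5. Say whether those values are pre-post or between-group effects.

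Because the SAP also reports a Bonferroni-adjusted alpha, state the number of tests and the effect detectable at that alpha.

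The cost is text only: no extra families and no change to any test. The stated sensitivity becomes less favourable unless a high baseline correlation can be justified.

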For African American men, prenatal engagement is an important prognosticator of things to come. Early Head Start Research and Evaluation Project data indicate that in contrast to White and Hispanic fathers, whose non-residential status at birth is the best predictor of the timing of eventual inaccessibility to their children, the best predictor for African American fathers is whether they were involved during the pregnancy, not non-residential status at birth (Lamb et al, 2009). Although African-American children are far more likely than Asian, Hispanic, or White children to know non-co-resident biological fathers (Avenilla et al., 2006), the nature of the coparenting alliance unmarried parents create (or fail to create) is a critical determinant of whether fathers stay involved. Coparenting between non-co-resident FFWB parents during infancy strongly predicted later father involvement, but early father involvement only weakly predicted later coparenting (Carlson et al., 2008). Prenatal fatherhood programs that promote father involvement without also helping mothers and fathers coordinate as coparents hence may also miss their mark (McHale, 2007; 2009); unwelcome father involvement triggers more, not less, coparenting conflict (Talbot et al., 2009). In the lone fatherhood intervention study examining both father involvement and coparenting as distinct outcomes, Doherty (2005) found desired intervention effects on early father engagement -- but no effect on coparenting.

In Pro00004412 (supported by funding from the Brady Education Foundation), we established that the FIOC intervention successfully promoted improvements in unmarried African American parents' rapport, problem-solving and communication. In Pro00019385, New Applications for Promoting Coparenting Alliances in Unmarried Couples, we established the feasibility of successfully delivering the intervention with positive outcomes to parents positive for minimal (or situational) intimate partner violence (IPV). The NIH study protocol (assessment, intervention, safety plan) diverges very little from the prior studies. The main difference is more extensive pre- and post- assessments and, of course, random selection for participation in the experimental group to receive the FIOC intervention. Any referred families with more significant and serious IPV are ineligible for participation in the study, as they were in the prior projects.

3. Research questions, objectives and purpose:

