All participants will share the potential to benefit from reflecting on the factors that promote their baby's adjustment (and from the coherence provided by the framework of the study) from their time of enrollment through the post-intervention follow up. Analyses of data collected in Pro00004412 indicated that participant couples showed improvements in rapport, problem-solving and communication, reductions in coparenting conflict, reductions in maternal depression, and improvements in views of fathers' roles and responsibilities. Some families also voiced appreciation knowing that findings from the study might benefit other non-co-resident parents like them planning ahead for life of their baby. In addition to the anticipated educational and intervention-based benefits study participants accrue, information from the study about benefits of interventions for unmarried parents having their first baby together will be of further help to Pinellas County agencies providing services to at-risk parents, to parents, and most of all to infants, by significantly enhancing environmental supports during the baby's first months of life. Program planners and others in the position to develop services for families outside of Pinellas will also benefit.

12. Human subjects considerations including a description of the informed consent process:

Participants who indicate interest after learning of the study from community partners are contacted by project staff and given details of study participation. Mothers who continue to express interest in the study are asked by project staff to notify fathers and provide contact information if fathers express interest. When so requested, staff meet individually at either

parent's residence or elsewhere agreed upon to provide specific details of the project and answer the parent's (and if appropriate, the LAR's) questions about the study. Female staffer will meet with both parents and male staffer will join her for the visit of the father, if deemed beneficial and/or desired by the participants. Informed consent for the participating mother and father is obtained only later, at the time they appear for their intake assessment session.

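### The statement that the trial can establish FIOC's effect on 10 of 12 SCID variables sets a between-arm threshold against pilot effects described only as improvement in participating couples, with no allowance for change under TAU

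*Protocol*

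**What the plan says.** Protocol Section 5 plans for N = 120 after attrition, "60 each in the treatment and control groups, respectively". With "alpha set at .05 and power of .8", it reports an F(1, 117) "of 7.74 with a $d = .514$ is required for significance". At power .5 it gives F = 4.03 and d = .37. It then turns to the feasibility study's effect sizes and says that even at the lower power "we would be positioned to establish the effect of the FIOC treatment for 10 of the 12 FIOC variables". The support offered is that 10 of the 12 SCID variables had a pilot d above .33.

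The protocol describes the feasibility results in four other places:

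- Section 4, measure 6 (coparenting discussions): "In the feasibility study, statistically-significant improvements were seen in SCID ratings of (increased) problem-solving communication", followed by increased cohesion and decreased coerciveness.
- Section 11: "Analyses of data collected in Pro00004412 indicated that participant couples showed improvements in rapport, problem-solving and communication".
- Section 2, comparing this trial with the earlier projects: "The main difference is more extensive pre- and post- assessments and, of course, random selection for participation in the experimental group".
- Section 14: the title of the cited pilot report speaks of improvements following the intervention.

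Hypothesis 1 in Section 3 is a contrast with TAU families. The SAP says that for Aims 1-4 a "two-sided independent sample t-test for equivalence will first be employed for single time point comparisons", with model-based analyses to follow. It gives no effect-size rationale of its own.

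**The concern.** The two quantities compared in Section 5 do not appear to be of the same kind. The thresholds .514 and .37 are differences between two arms of 60. The pilot d values, as far as the protocol describes them, measure change in couples who all received FIOC. Such a change contains the FIOC effect together with whatever would also have happened without it: repeating the discussion task, regression to the mean, and the progress of the pregnancy. In this trial TAU families repeat the same discussions at baseline, 3 and 12 months, and they receive county services and a Navigator (Sections 1 and 4). Zero change in that arm is an assumption that Section 5 neither states nor defends.

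What is at stake is the stated prospect of success. The pilot comparison is the only effect-size rationale in either document. It is a separate matter from two other weaknesses in the same sentence: the count uses .33 where the threshold is .37, and the power level is 50%. Repairing both would still leave change in treated couples standing in for a treatment difference.

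**Working it through.** **Inputs.** From Section 5: 60 per arm, alpha .05, d = .514 and .37, F(1, 117) = 7.74 and 4.03, and a pilot cut-off of .33. From the SAP: two-sided testing. Not given in the documents: the 12 pilot d values, how they were standardised, whether the pilot had a comparison group, and the change expected under TAU.

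**Step 1: reproduce the plan's figures.** With equal arms, d = 2√(F/df).

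- 2√(7.74/117) = .514
- 2√(4.03/117) = .371

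Power comes from the noncentral F distribution with (1, 117) df, noncentrality λ = d² × 60 × 60/120 = 30d², and critical F = 3.92.

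- d = .514: λ = 7.93, power .797 (plan: .80)
- d = .37: λ = 4.11, power .520 (plan: .50)

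Solving for d gives .516 at 80% power and .361 at 50%. The plan's arithmetic is sound to rounding, and it confirms that these are between-arm effects. At the .33 used for the count, λ = 3.27 and power is .43, even if the pilot value is taken at face value.

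**Step 2: what links a pilot d to the trial's d.** If the pilot d is a pre-post change scaled by the same SD as the trial's d, then

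between-arm d = pilot d × (1 − k),

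where k is the TAU change as a fraction of the pilot change. Section 5 uses the pilot d unchanged, which amounts to k = 0.

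**Step 3: power under assumed k.** The values of k are illustrations; neither document supports a particular one. The last column assumes adjustment for baseline with a baseline-outcome correlation of r = .5, so the effective d is divided by √(1 − .25) = .866.

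| Pilot d | k | Between-arm d | Power, unadjusted | Power, adjusted (r = .5) |
|---|---|---|---|---|
| .37 | 0 | .37 | .52 | .64 |
| .37 | .25 | .28 | .33 | .41 |
| .37 | .50 | .19 | .17 | .21 |
| .514 | 0 | .514 | .80 | .90 |
| .514 | .25 | .39 | .55 | .68 |
| .514 | .50 | .26 | .29 | .36 |

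**Step 4: the other direction.** If TAU families worsened by a quarter of the pilot change (k = −.25), a pilot d of .37 would become .37 × 1.25 = .4625. Then λ = 30 × .4625² = 6.42 and unadjusted power is .71. A large pilot d also survives a substantial TAU change: .80 × .5 = .40, still above .37. The number of variables that would drop out of the 10 cannot be computed without the values themselves.

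**The case against.** **The single-arm pilot is inferred.** This stands. The protocol does not say that the pilot lacked a control group or how d was computed, and the summary of the 12 values to which Section 5 refers is not in the document. The four descriptions agree with one another and none points to a comparison group, but that falls short of a statement of design. If the pilot values were controlled, one sentence saying so would answer the point.

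**A reader might infer that the 10-of-12 claim holds only if TAU families do not improve at all.** The documents do not support that. Section 5 gives only a lower bound for the pilot values, so some may be large enough to stay above the threshold after subtracting a TAU change, and TAU families could also deteriorate between pregnancy and 12 months.

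**A reader might infer that the claim distorts what a null result can exclude.** It does not. That depends on the sample size, the variability and the resulting confidence interval, not on pilot effects, and the detectable d is already stated correctly.

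**A reader might suppose that a d scaled by the SD of change necessarily flatters the trial.** That does not follow either. The conversion to raw-score units depends on the pre-post correlation: above .5 it lowers d and below .5 it raises it. Adjustment for baseline offsets the loss where there is one. The scale is a reason to report the formula, not a source of a fixed correction.

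**The planned analysis may be more powerful than a t-test.** This is fair. The SAP plans repeated-measures ANCOVA for outcomes measured at all three visits, as the SCID discussions are. It does not name baseline as the covariate, and t-tests come first. Adjustment raises every figure in the table, but it does not supply the missing TAU term.

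**Conclusion.** The concern holds in a limited form. The detectable-effect arithmetic in Section 5 is right. The step from it to 10 of 12 variables is not supported as a FIOC-versus-TAU prospect, because no passage gives a FIOC-minus-TAU effect behind it and nothing is allowed for change under TAU.

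The size cannot be fixed from the documents. For a variable at the .37 threshold, a TAU change of 25% to 50% of the pilot change would take unadjusted power from .52 to between .33 and .17, or from .64 to between .41 and .21 with baseline adjustment at r = .5. These figures rest on the assumed fractions, on a common standardiser, and on the inference that the pilot values are uncontrolled. If TAU families worsened, the error would run the other way. The sample size, endpoints and analysis are unaffected; what needs correcting is the stated prospect of success.

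**What to change.** Amend Section 5 as follows:

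1. Remove the 10-of-12 statement, or keep it only if the pilot d values prove to be controlled between-group effects.
2. State that 60 per arm gives 80% power for a between-arm d of about .52 and 50% for about .36 (two-sided .05, unadjusted).
3. State the feasibility study's design, whether it had a comparison group, and how d was standardised.
4. Show power with TAU change set at 0, 25% and 50% of the pilot change, labelled as assumptions, both without adjustment and with baseline adjustment at a stated correlation.

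The cost is a rewording of one section, plus retrieval of the pilot design and d formula, which the study team should hold. The stated prospect of success becomes less favourable. Enrolment does not change.
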